5.3.3 Reference Standard and Comparators

There is little risk of reference standard bias in this study as a composite reference standard of phenotypic DST and NGS will be used for resistance detection (Table 1). The use of both phenotypic and genotypic information will ensure high confidence in the reference standard, as certain mutations (e.g. many *eis* promoter mutations) are known to confer only low-levels of phenotypic drug resistance, and so they may not be detected by phenotypic DST at only one critical concentration. Furthermore, all molecular assays evaluated in this study detect resistance-mutations in similar gene regions, and so all mutations that are detectable by the Xpert MTB/XDR assay are generally detected by NGS and/or the Hain LPAs and vice versa.

Table 1. Composite reference standard for diagnostic performance analysis

Composite Reference Standard		
Drug of Interest	NGS of Reference Gene(s)	MGIT960 Phenotypic DST
Isoniazid	katG , fabG1 , inhA promoter, ahpC promoter	Isoniazid
Ethionamide	inhA promoter	Ethionamide

Fluoroquinolones		
Moxifloxacin	gyrA, gyrB	Moxifloxacin
Levofloxacin	gyrA, gyrB	Levofloxacin
Second-line Injectables		
Amikacin	rrs	Amikacin
Kanamycin	rrs, eis promoter	Kanamycin
Capreomycin	rrs	Capreomycin

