9.2 Statistical Analysis Plan

The statistical analysis plan (SAP) will be developed and finalized before database lock and will describe the samples to be included in the analyses and procedures for accounting for missing, unused, and spurious data. This section is a summary of the planned statistical analyses of the primary and secondary endpoints.

Primary analyses of outcome data will be done using the composite reference standard. Primary analyses will be focused on estimating accuracy (clinical sensitivity and specificity) for INH and second-line drug resistance detection:

- **Clinical Sensitivity:** proportion positive by composite reference standard (phenotypic DST and NGS) that are detected as positive by index test (Xpert MTB/XDR)
- **Clinical Specificity:** proportion negative by composite reference standard (phenotypic DST and NGS) that are detected as negative by index test (Xpert MTB/XDR)

For simple proportions (sensitivity and specificity), 95% confidence intervals will be computed using the Wilson score method. Primary diagnostic accuracy analyses will be carried out across all study sites. All TB samples that generate both Xpert MTB/XDR and composite reference standard results will contribute to the analysis of the performance characteristics for INH- and second-line resistance detection. If discordances are observed between the Xpert MTB/XDR results from testing sputa and the culture isolate, results from the culture isolate will be considered in these analyses.

Primary analyses will also evaluate assay operational characteristics, which will be captured through direct observation and user-appraisal questionnaires. Primary assessments of Xpert MTB/XDR operational characteristics will evaluate assay characteristics compared to Hain MTBDR*plus/sl* assays, including:

- Time to first result
- Ease of use
- Failure and invalid rate

These assessments of Xpert and LPA characteristics will be descriptive, and any differences will be further explored by sample type (i.e. smear- and culture-result, patient HIV- and treatment statuses, etc.). Assessments of platform operational characteristics will be based upon information gathered during the clinical study, as well as information provided by the manufacturers.

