9.2.2 Definitions for Diagnostic Performance Analysis

TEST RESULT	DESCRIPTION
Phenotypic Drug*-resistant	Culture-positive and growth for Drug* in conventional DST testing.
Phenotypic Drug*-sensitive	Culture-positive and no growth for Drug* in conventional DST testing
Genotypic Drug*-resistant	NGS identifies mutations recognized to be associated with resistance (defined based on consultation with WHO prior to analysis)
Genotypic Drug*-sensitive	NGS identifies no mutations recognized to be associated with resistance (defined based on consultation with WHO prior to analysis)
Composite reference standard Drug*-resistant	If Phenotypic Drug*-sensitive but NGS identifies mutations recognized to be associated with Drug* resistance for the respective gene regions, the composite reference standard will be considered Drug*-resistant. If Phenotypic Drug*-resistant but NGS does not identify mutations recognized to be associated with Drug* resistance for the respective gene regions, the composite reference standard will be considered Drug*-resistant (as mutations will be assumed outside of the region sequenced).

Composite reference standard Drug*-sensitive | If Phenotypic Drug*-sensitive and NGS shows either no mutations or only mutations that are not associated with Drug* resistance for the respective gene regions.

* Drug: INH, ETH, FQ (moxifloxacin and levofloxacin for phenotypic DST), AMK, KAN or CAP

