3.2 Analysis datasets

Describe the datasets that will be used in the analysis, like the examples below.

- ITT (Intention-To-Test) all subjects successfully enrolled in the study

- MITT (Modified-Intention-To-Test) all subjects in ITT for whom at least one test result is available, but not all (e.g. composite reference missing)
- PP (Per-Protocol) all subjects in ITT for whom results for all tests (Xpert MDR/XDR and composite reference standards) are available (complying with the protocol)
- QUEST (Questionnaire evaluation) all personnel who provided valid responses to the Xpert MTB/XDR Clinical Study User Appraisal Questionnaire

Samples meeting any of the following criteria in the course of the study will be excluded from the primary analyses of Xpert MTB/XDR accuracy:

- no valid result for NGS for relevant gene region or Xpert MTB/XDR,
- smear-positive/culture negative,
- single positive culture with ≤ 20 colonies (LJ) or time to positivity > 28 days (MGIT),
- culture positive but no MTB complex identification available,
- specimens with growth of mycobacteria other than MTB complex only

4 Description of statistical methods

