4.2 Analysis of the primary outcome(s)

The primary objectives 1.1, 1.2 and 1.3 will be analysed with the methodology described in section 4.1.

Outcome 1.1

Estimates of sensitivity and specificity of Xpert MTB/XDR will be calculated, for INH and ETH resistance detection with phenotypic DST and *katG*, *fabG1*, *ahpC* and *inhA* sequencing results as a composite reference standard (see Appendix). This outcome will be evaluated on the PP population.

Outcome 1.2

Estimates of sensitivity and specificity of Xpert MTB/XDR will be calculated, for fluoroquinolone resistance detection, with phenotypic DST and *gyrA* and *gyrB* sequencing results as a composite reference standard (see Appendix). This outcome will be evaluated on the PP population.

Outcome 1.3

Estimates of sensitivity and specificity of Xpert MTB/XDR will be calculated, for second-line injectable resistance detection, with phenotypic DST and *rrs* and *eis* sequencing results as a composite reference standard (see Appendix). This outcome will be evaluated on the PP population.

Outcome 1.4

Assess Xpert MTB/XDR operational aspects and ease of use, including Xpert MTB/XDR non-determinant rates.

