The results will serve as an early indicator of Xpert MTB/XDR accuracy in the clinical trial. If performance estimates fall outside of the presented confidence intervals for resistance detection (Table 2), the Data Monitoring Committee (DMC) will review all data for accuracy and consistency. Additionally, the sponsor may conduct a monitoring visit to one or more sites to ensure adherence to SOPs and effective data management.

7 Additional sub-group analyses

Subgroups analyses, and definitions of subgroups, are described in section 4.3. No additional subgroup analyses will be performed.

8 Multiple comparisons/multiplicity adjustments

No multiple testing of statistical hypotheses is going to be performed.

9 Exploratory analyses

No exploratory analyses will be performed.

10 Sample size

To achieve the targeted precision for accuracy estimates, it is estimated that 760 samples will need to be tested for this study, with a final 284 MTB-positive and an additional 316 RIF-resistant samples tested by Xpert MTB/XDR and all reference standards and comparators, i.e. a total of 600 specimen results available for analysis. The desired precision for the accuracy estimates was chosen to achieve high confidence in the estimates for Xpert MTB/XDR resistance detection when considering evidence from both the 'external laboratory validation' (phase I) and the clinical trial (phase II). The sample size is detailed below in Table 2.

		n	Point estimate (95%CI) *	Total width of CI *
INH	Sensitivity	395	90% (86, 93)	7%
	Specificity	205	98% (95, 99)	4%
FQs	Sensitivity	93	90% (82, 95)	13%
	Specificity	507	98% (96, 99)	3%
AMK	Sensitivity	34	90% (74, 97)	23%
	Specificity	566	98% (96, 99)	3%
KAN	Sensitivity	71	90% (80, 96)	16%
	Specificity	529	98% (96, 99)	3%
CAP	Sensitivity	34	90% (74, 97)	23%
	Specificity	566	98% (96, 99)	3%

Table 2 Sample size

* 95%CI based on Wilson's score method (as recommended by Newcombe et al. as well as CLSI/FDA) using continuity correction.

11 Minimization of error and bias

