11.1 Enrolment and randomization procedures

Describe how enrolment will be carried out (from the clinical protocol) and add details on the randomization procedure (if applicable)

12 Case definitions

Table 3 describes the categorization of results based on test results.

TEST RESULT	DESCRIPTION
Phenotypic Drug*-resistant	Culture-positive and growth for Drug* in conventional DST testing.
Phenotypic Drug*-sensitive	Culture-positive and no growth for Drug* in conventional DST testing
Genotypic Drug*-resistant	NGS identifies mutations recognized to be associated with resistance (defined based on consultation with WHO prior to analysis)
Genotypic Drug*-sensitive	NGS identifies no mutations recognized to be associated with resistance (defined based on consultation with WHO prior to analysis)
Composite reference standard Drug*-resistant	If Phenotypic Drug*-sensitive but NGS identifies mutations recognized to be associated with Drug* resistance for the respective gene regions, the composite reference standard will be considered Drug*-resistant. If Phenotypic Drug*-resistant but NGS does not identify mutations recognized to be associated with Drug* resistance for the respective gene regions, the composite reference standard will be considered Drug*-resistant (as mutations will be assumed outside of the region sequenced).
Composite reference standard Drug*-sensitive	If Phenotypic Drug*-sensitive and NGS shows either no mutations or only mutations that are not associated with Drug* resistance for the respective gene regions.

* Drug: INH, ETH, FQ (moxifloxacin and levofloxacin for phenotypic DST), AMK, KAN or CAP

Table 3 Case definitions

13 Statistical software

The analysis will be performed using the R statistical language (version 3.4.0 or higher) on OsX, and Microsoft Excel 2018 (version 16.16 or higher).

14 References

Add required references.

15 Document history

Version	Notes / Changes
1.0	Initial version

16 Appendix

The definitions of composite reference standards are given in table 4.

DRUG RESISTANCE	COMPOSITE REFERENCE STANDARD
INH-resistant	NGS of katG , fabG1 , ahpC and inhA detects ≥ 1 mutation associated with INH resistance and MGIT culture is INH drug-resistant at the critical concentration.
ETH-resistant	NGS of inhA detects ≥ 1 mutation associated with ETH resistance and MGIT culture is ETH drug-resistant at the critical concentration.

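### The SAP's primary analyses cite a reference standard (Table 4) that requires DST and NGS to agree, which contradicts Protocol 9.2.2 and SAP Table 3 and leaves discordant samples without a class

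*SAP*

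**What the plan says.** For each of outcomes 1.1, 1.2 and 1.3, SAP 4.2 names phenotypic DST and "sequencing results as a composite reference standard (see Appendix"), to be evaluated on the PP set. SAP 3.2 defines that set as "all subjects in ITT for whom results for all tests (Xpert MDR/XDR and composite reference standards) are available".

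The Appendix (SAP 16) holds Table 4, titled as the definition of the composite reference standards. Its INH-resistant row applies when NGS "detects ≥ 1 mutation associated with INH resistance and MGIT culture is INH drug-resistant at the critical concentration". The ETH, FQ, AMK, KAN and CAP rows have the same form. The susceptible rows require no associated mutation and a susceptible MGIT result.

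SAP 12, Table 3, which 4.2 does not cite, repeats the text of Protocol 9.2.2. A DST-sensitive sample with a recognised mutation is resistant. So is the opposite pattern, introduced in the protocol by "If Phenotypic Drug*-resistant but NGS does not identify mutations recognized to be associated with Drug* resistance for the respective gene regions": in that case "the composite reference standard will be considered Drug*-resistant (as mutations will be assumed outside of the region sequenced"). A sample is sensitive only if both tests are negative.

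Protocol 5.3.3 explains why a composite is used: some mutations, with many in the eis promoter as the example, confer only low-level resistance, "so they may not be detected by phenotypic DST at only one critical concentration". Protocol 9.2 adds: "All TB samples that generate both Xpert MTB/XDR and composite reference standard results will contribute to the analysis". SAP 10 plans on all samples having a class: "i.e. a total of 600 specimen results available for analysis".

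**The concern.** The SAP contains two definitions of the primary reference standard, and the primary analyses cite the one that differs from the protocol. Protocol 9.2.2 and SAP Table 3 use an OR rule (either test resistant). Table 4 uses an AND rule (both resistant), with both tests negative for susceptible. A sample on which DST and NGS disagree therefore has no class under Table 4. Since the PP set needs a composite result, the sample leaves the sensitivity denominator by implication, although no exclusion rule says so.

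Two kinds of sample are lost, and they pull in opposite directions. DST-resistant samples without a mutation in the target regions are likely misses for an assay that reads those regions, so losing them raises sensitivity. DST-sensitive samples with a resistance mutation are likely to be detected, so losing them lowers it. The second kind includes the cases that Protocol 5.3.3 gives as a reason for having a composite.

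**Working it through.** **1. The four cells under each rule.**

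| DST | NGS | Protocol 9.2.2 / SAP Table 3 | SAP Table 4 |
|---|---|---|---|
| Resistant | Mutation | Resistant (implied, not written out) | Resistant |
| Resistant | No mutation | Resistant | No class |
| Sensitive | Mutation | Resistant | No class |
| Sensitive | No mutation | Sensitive | Susceptible |

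The bottom row is the same under both rules. The reference-susceptible set, and so specificity, does not depend on the AND/OR choice.

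**2. Does other text place the discordant samples?** The exclusion lists in Protocol 9.2.1 and SAP 3.2 do not name DST/NGS discordance. The discordance text in Protocol 5.3.2, 7.1 and 9.2 concerns disagreements that involve Xpert MTB/XDR results. It assigns no reference status when DST and NGS disagree.

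**3. The plan's own denominators.** From Protocol Appendix 4, with 284 MTB-positive and 316 additional RIF-resistant samples, the expected resistant counts are:
- INH: 284 × 0.29 + 316 × 0.99 = 395.2 (stated 395)
- FQ: 284 × 0.05 + 316 × 0.25 = 93.2 (stated 93)
- AMK/CAP: 284 × 0.02 + 316 × 0.09 = 34.1 (stated 34)
- KAN: 284 × 0.01 + 316 × 0.215 = 70.8 (stated 71)

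The continuity-corrected Wilson intervals at 90% also reproduce within rounding: FQ 81.6 to 95.0, KAN 80.0 to 95.5, AMK/CAP 73.7 to 97.1. Resistant plus sensitive counts equal 600 for all five drugs in Table 2: 395 + 205, 93 + 507, 34 + 566 (AMK and CAP), 71 + 529. The 21% allowance for losses is 1% invalid, 10% contaminated and 10% non-determinant, with nothing for discordance.

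**4. Effect on sensitivity.** The documents give no discordance rates, so these are assumptions:
- Sensitivity under the OR rule is 90%.
- A share d of OR-resistant samples is DST-resistant without a mutation, all missed (so d is at most 10%).
- A share e is DST-sensitive with a mutation, all detected.

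Sensitivity under Table 4 = (0.90 − e) / (1 − d − e).

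| d | e | Sensitivity under Table 4 |
|---|---|---|
| 2% | 0 | 0.90/0.98 = 91.8% |
| 5% | 0 | 0.90/0.95 = 94.7% |
| 8% | 0 | 0.90/0.92 = 97.8% |
| 5% | 5% | 0.85/0.90 = 94.4% |
| 0 | 10% | 0.80/0.90 = 88.9% |
| 2% | 10% | 0.80/0.88 = 90.9% |
| 5% | 10% | 0.80/0.85 = 94.1% |

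The result exceeds 90% only if 0.9d > 0.1e, that is e < 9d. At d = 2% the break-even is e = 18%.

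**5. Compared with planned precision.** Half of the stated Table 2 width is 3.5 points for INH, 6.5 for FQ, 8 for KAN and 11.5 for AMK/CAP. With e = 0, the shift equals these at:
- INH: d = 1 − 0.90/0.935 = 3.7%
- FQ: d = 1 − 0.90/0.965 = 6.7%
- KAN: d = 1 − 0.90/0.98 = 8.2%
- AMK/CAP: not reachable, since the shift cannot exceed 10 points

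**6. Samples lost.** At d = e = 5%, 10% of the resistant samples have no class: about 40 of 395 (INH), 9 of 93 (FQ), 7 of 71 (KAN) and 3 of 34 (AMK/CAP). Table 2 has no ETH row, so no count is given for ETH.

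**7. Scope differences, separate from AND/OR.**
- Table 4 defines FQ by moxifloxacin alone; SAP Table 3 and Protocol Table 1 also list levofloxacin. As an illustration, suppose 2 of the 93 were resistant to levofloxacin only, mutation-negative and missed. They would become reference-susceptible. Sensitivity would go from 84/93 = 90.3% to 84/91 = 92.3%, and specificity from 497/507 to 499/509, both 98.0%.
- Table 4 lists eis for AMK; Protocol Table 1 and Appendix 5 list rrs only. As only AMK-associated mutations count, this probably has little effect.

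**The case against.** The strongest reply is that the two SAP tables complement each other. Table 3 writes out the discordant patterns, Table 4 the concordant one, their susceptible rules agree, and together they classify all four cells without conflict. The PP definition asks that results be available, not that DST and NGS agree, and Protocol 9.2 favours keeping every sample. A careful analyst would then reach the OR rule.

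That is a fair account of what was probably intended, but no text says it. SAP 4.2 cites only the Appendix, and Table 4 presents itself as the definition. Combining the tables would also leave the moxifloxacin-only FQ rule in conflict with Protocol Table 1. The denominator of a primary endpoint should not rest on an unstated reading.

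Three narrower objections have some force:
- The totals of 600 arise by construction, because Appendix 4 takes sensitive counts as complements of assumed prevalences. They do not show which rule was meant. They show only that no unclassified group was planned for.
- The direction is not certain, and least so for KAN. In the RIF-resistant group Appendix 4 expects 68 KAN-resistant and 28 AMK/CAP-resistant samples, so at least 68 − 28 = 40 are KAN-resistant without AMK resistance. The documents do not say how many of these are DST-sensitive. With a large e, say d = 2% and e = 30%, Table 4 gives 0.60/0.68 = 88.2%, a downward shift.
- Specificity is unchanged only if discordant samples stay unclassified. Coding DST-sensitive, mutation-positive samples as susceptible would lower it, but Table 4 does not provide for that.

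**Conclusion.** The concern holds and must be fixed before database lock. SAP 4.2 ties outcomes 1.1 to 1.3 to a definition that differs from Protocol 9.2.2 and from the SAP's own Table 3, and that gives DST/NGS-discordant samples no class. This rests on the text alone.

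The size rests on assumed rates. From 90% under the OR rule, the scenarios tabulated above run from 88.9% to 97.8%. The shift is upward whenever e is below 9d, so upward is more likely overall, with KAN the least certain. For INH, a d of about 3.7% with e = 0 is enough to move the estimate by half the planned interval width. The AND/OR choice leaves specificity as it is. The FQ scope mismatch is a smaller, separate error, and the AMK mismatch is probably only wording.

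**What to change.** - Replace the resistant rows of SAP Table 4 with the OR rule of Protocol 9.2.2 and SAP Table 3, writing out all four cells: both resistant, DST only and NGS only are resistant; both negative is susceptible.
- Point SAP 4.2 to that single definition.
- Align the FQ and AMK rows with Protocol Table 1. For FQ, state whether moxifloxacin and levofloxacin are analysed separately, as their separate rows there suggest, or give the rule that combines them.
- Report, per drug, the count of each discordant pattern with its Xpert MTB/XDR result.
- Label any concordant-only estimate as a sensitivity analysis.

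The cost is SAP wording and one discordance table per drug, from data already collected. Reported sensitivity may be less favourable than under Table 4, by an amount that depends on the discordance rates.
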